4. TREATMENT PLAN

4.1. Study Design

This is a phase II study employing a 2-stage design to evaluate the primary endpoint of ORR to combination therapy with nivolumab 3 mg/kg administered intravenously (IV) every 2 weeks with ipilimumab 1 mg/kg administered IV every 6 weeks in patients with advanced NSCLC and primary resistance to anti-PD-1 axis therapy. If there is at least 1 response or prolonged stability (≥ 24 weeks) using irRC appreciated in the first 10 patients who initiate trial therapy, an additional 30 patients will be enrolled to a total of 40 patients. An additional 10 patients with acquired resistance to anti-PD-1 axis therapy will be enrolled in an exploratory cohort receiving the same therapy.

4.1.1. Tumor Biopsies and Pharmacodynamic Blood Draws

A trial tumor biopsy will be required of all enrolled patients before starting treatment. A second mandatory tumor biopsy will be performed between day 56 and 70 of trial therapy (9-10 weeks after initiation of therapy). These on-trial tumor biopsies must be collected via core, forceps, or incision/ excision. Although the second biopsy will generally be obtained from the same site as the first one, there may be circumstances when another tumor site would alternatively be biopsied (e.g. lesion initially biopsied becomes too small to safely and/or effectively biopsy).

Optional biopsies may be performed at sites of response (including partial response, or stable disease at least 24 weeks) or progression while on treatment. We anticipate that such biopsies will help to characterize changes in the tumor immune microenvironment that play a role in mitigating response or resistance to treatment, respectively.

If archived tumor tissue from a biopsy performed prior to enrollment is available, unstained slides or block will be requested for additional analysis of biomarkers (as consented to in the informed consent document).

Blood draws to characterize the peripheral anti-tumor immunologic milieu will be collected prior to the initiation of combination therapy. Serial draws will be performed 2 weeks, 4 weeks, 6 weeks, and 9 weeks after the initiation of therapy (should correspond with timing of on-treatment biopsy) as well as at the time of disease progression.

4.2. Description, packaging, labeling and storage of study drugs

Table 4.2: Study Drugs

| Product Description / Class and Dosage Form | Potency | IP/Non-IMP | Blinded or Open Label | Packaging / Appearance | Storage Conditions (per label) |
|--|-------------------|----------------------------|-------------------------------|--|--|
| Nivolumab Solution for Injection | 100 mg (10 mg/mL) | 10 mL per vial/ Open-label | 5 per carton/ Open-label | Clear to opalescent colorless to pale yellow liquid. May contain particles | 2 to 8° C. Protect from light and freezing |
| Ipilimumab Solution for Injection | 200 mg (5mg/mL) | 40 mL vial/Open-label | 4 vials per carton/Open-label | Clear to opalescent colorless to pale yellow liquid. May contain particles | 2 to 8° C. Protect from light and freezing |

4.3. Treatment Schedule and Dosing Plan

Enrolled subjects will receive treatment with nivolumab 3 mg/kg as a 30-minute infusion every 2 weeks and ipilimumab 1 mg/kg as a 30-minute infusion every 6 weeks, starting on Day 1, until progression, unacceptable toxicity, withdrawal of consent, or the study ends, whichever occurs first.

When nivolumab and ipilimumab are to be administered on the same day, separate infusion bags and filters must be used for each infusion. Nivolumab is to be administered first. The second infusion will always be ipilimumab and will start no sooner than 30 minutes after completion of the nivolumab infusion.

Nivolumab and ipilimumab may be diluted in 0.9% Sodium Chloride Solution or 5% Dextrose solution.

Dosing calculations should be based on the body weight assessed. If the subject's weight on the day of dosing differs by >10% from the weight used to calculate the prior dose, the dose must be recalculated. All doses should be rounded to the nearest milligram. There will be no dose modifications allowed.

Subjects may be dosed with nivolumab no less than 12 days from the previous dose. There are no premedications recommended.

Subjects should be carefully monitored for infusion reactions. If an acute infusion reaction is noted, subjects should be managed according to Section 4.8.5.

Doses of nivolumab and/or ipilimumab may be interrupted, delayed, or discontinued depending on how well the subject tolerates the treatment.

4.3.1. Dose Delay Criteria

Dose delay criteria apply to all drug-related AEs. Treatment delays are allowable up to 6 weeks for nivolumab and 12 weeks for ipilimumab from the last dose (any dose delays greater than this will require approval from the medical monitor).

Tumor assessments for all subjects should continue as per protocol **even if dosing is delayed**.

Nivolumab and ipilimumab administration should be delayed for the following:

- Grade 2 non-skin, drug-related adverse event, except for fatigue and laboratory abnormalities
- Grade 2 drug-related creatinine, AST, ALT and/or Total Bilirubin abnormalities
- Grade 3 skin, drug-related AE
- Grade 3 drug-related laboratory abnormality with the following exceptions:
 - Grade 3 lymphopenia or asymptomatic amylase or lipase elevation does not require dose delay
 - Grade ≥ 3 AST, ALT, Total Bilirubin will require dose discontinuation
 - Any AE, laboratory abnormality or intercurrent illness which, in the judgment of the investigator, warrants delaying the dose of study medication.

Participants who have drug-related toxicities that meet the criteria for dose delay should have both drugs (ipilimumab and nivolumab) delayed until retreatment criteria are met. (Exceptions apply to the retreatment criteria after dose delay of ipilimumab and nivolumab for Grade ≥ 3 amylase and lipase abnormalities that are not associated with symptoms or clinical manifestations of pancreatitis and that are attributed to ipilimumab alone.)

Rescheduling:

Nivolumab may be delayed until the next planned ipilimumab dose if the next ipilimumab dose is scheduled within the next 12 days. This will permit periodic ipilimumab dosing to be synchronized with nivolumab dosing.

Ipilimumab should be dosed at the specified interval regardless of any delays in intervening nivolumab doses. However, in order to maintain periodic synchronized dosing of ipilimumab and nivolumab, the dosing days of nivolumab (every 2 weeks ± 3 days) and ipilimumab (every 6 weeks ± 5 days) may be adjusted within the permitted ± 5 day window, as long as consecutive nivolumab doses are given at least 12 days apart. Ipilimumab may be delayed beyond the 5 day window if needed to synchronize with the next nivolumab dose.

If an ipilimumab dose is delayed beyond 6 weeks from the prior ipilimumab dose, then subsequent ipilimumab doses should be rescheduled to maintain the 6 week interval between consecutive ipilimumab doses.

A dose delay of ipilimumab which results in no ipilimumab dosing for > 12 weeks requires ipilimumab discontinuation, with exceptions as noted in Section 4.3.3.2.

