4.3.3. Criteria to Resume Dosing

4.3.3.1 Criteria to Resume Nivolumab Dosing

Subjects may resume treatment with nivolumab when the drug-related AE(s) resolve(s) to Grade \leq 1 or baseline, with the following exceptions:

- Subjects may resume treatment in the presence of Grade 2 fatigue.
- Subjects who have not experienced a Grade 3 drug-related skin AE may resume treatment in the presence of Grade 2 skin toxicity.
- For subjects with Grade 2 AST, ALT, or Total bilirubin elevations, dosing may resume when laboratory values return to baseline and management with corticosteroids, if needed, is complete.
- Subjects with combined Grade 2 AST/ALT AND total bilirubin values meeting discontinuation parameters (see package insert) should have treatment permanently discontinued.
- Drug-related pulmonary toxicity, diarrhea, or colitis must have resolved to baseline before treatment is resumed. Subjects with persistent Grade 1 pneumonitis after completion of a steroid taper over at least 1 month may be eligible for retreatment if discussed with and approved by the PI.
- Subjects with Grade 1-3 drug-related endocrinopathies adequately controlled with only physiologic hormone replacement may resume treatment after consultation with the PI
- Subjects who received systemic corticosteroids for management of any drug-related toxicity must be off corticosteroids or have tapered down to an equivalent dose of prednisone \leq 10 mg/day.
- Participants who delay study treatment due to any Grade \geq 3 amylase or lipase abnormality that is not associated with symptoms or clinical manifestations of pancreatitis, and that is assessed by the investigator to be related to ipilimumab and not to nivolumab, may resume nivolumab when the amylase or lipase abnormality has resolved to Grade < 3. The PI should be consulted prior to resuming nivolumab in such participants.
- Dose delay of nivolumab that results in treatment interruption of > 6 weeks requires treatment discontinuation, with exceptions as noted in Section 4.3.4.
- One exception to note is when ipilimumab and nivolumab doses are delayed due to drug-related Grade \geq 3 amylase or lipase abnormalities not associated with symptoms or clinical manifestations of pancreatitis. If the investigator assesses the Grade \geq 3 amylase or lipase abnormality to be related to ipilimumab and not related to nivolumab, nivolumab may be

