Grade \geq 3 amylase or lipase abnormalities not associated with symptoms or clinical manifestations of pancreatitis. If the investigator assesses the Grade \geq 3 amylase or lipase abnormality to be related to ipilimumab and not related to nivolumab, nivolumab may be resumed when the amylase or lipase abnormality resolves to Grade $<$ 3 but ipilimumab may only be resumed when the amylase or lipase abnormality resolves to Grade 1 or baseline. Investigator attribution of this toxicity to the ipilimumab dosing must be clearly noted in the participant's medical chart. The PI should be consulted prior to resuming nivolumab in such participants.

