4.3.4.1. Nivolumab or Ipilimumab Dose Discontinuation

Treatment with nivolumab or ipilimumab must be permanently discontinued for any of the following:

- Any Grade 2 drug-related uveitis or eye pain or blurred vision that does not respond to topical therapy and does not improve to Grade 1 severity within the re-treatment period OR requires systemic treatment
- Any Grade 3 non-skin, drug-related adverse event lasting $>$ 7 days, or recurs with the following exceptions for laboratory abnormalities, diarrhea, drug-related uveitis, pneumonitis, bronchospasm, hypersensitivity reactions, infusion reactions, and endocrinopathies:
 - Grade 3 drug-related diarrhea, colitis, neurologic toxicity, uveitis, pneumonitis, bronchospasm, hypersensitivity reaction, or infusion reaction of any duration requires discontinuation
 - Grade 3 drug-related endocrinopathies, adequately controlled with only physiologic hormone replacement do not require discontinuation. Adrenal insufficiency requires discontinuation regardless of control with hormone replacement.
 - Grade 3 drug-related laboratory abnormalities do not require treatment discontinuation except:
 - Grade 3 drug-related thrombocytopenia $>$ 7 days or associated with bleeding requires discontinuation.
 - Any drug-related liver function test (LFT) abnormality that meets the following criteria require discontinuation:
 - Grade \geq 3 drug-related AST, ALT or Total Bilirubin requires discontinuation. In most cases of Grade 3 AST or ALT elevation, study drug(s) will be permanently discontinued. If the investigator determines a possible favorable benefit/risk ratio that warrants continuation of study drug(s), a discussion between the investigator and the PI must occur.
 - Concurrent AST or ALT $>$ 3 x ULN and total bilirubin $>$ 2x ULN
- Any Grade 4 drug-related adverse event or laboratory abnormality (including but not limited to creatinine, AST, ALT, or Total Bilirubin), except for the following events which do not require discontinuation:

- Grade 4 neutropenia \geq 7 days
- Grade 4 lymphopenia or leukopenia
- Isolated Grade 4 electrolyte imbalances/abnormalities that are not associated with clinical sequelae and are corrected with supplementation/appropriate management within 72 hours of their onset

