5.4. STUDY CALENDAR

| W (week) | Pre-Tx | W 1 | W 2 | W 3 | W 4 | W 5 | W 6 | W 7 | W 8 | W 9 | W 10 | W 11 | W 12 | W 13 | W 14 | W 15 | W 16 | W 17 & Q2W | End of Tx |
|------------------------------|--------|-----|-----|-----|-----|-----|-----|-----|-----|-----|------|------|------|------|------|------|------|-------------|------------|
| Nivolumab | | X | | X | | X | | X | | X | | X | | X | | X | | X | |
| Ipilimumab | | X | | | | | | X | | | | | | X | | | | | W 19 & Q6W |
| Informed Consent | X | | | | | | | | | | | | | | | | | | |
| Demographics | X | | | | | | | | | | | | | | | | | | |
| Medical History | X | | | | | | | | | | | | | | | | | | |
| Concurrent Meds | X | X | | X | | X | | X | | X | | X | | X | | X | | X | X |
| Physical Exam | X | X | | X | | X | | X | | X | | X | | X | | X | | X | X |
| Vital Signs ¹ | X | X | | X | | X | | X | | X | | X | | X | | X | | X | X |
| Height | X | | | | | | | | | | | | | | | | | | |
| Weight | X | X | | X | | X | | X | | X | | X | | X | | X | | X | X |
| ECOG PS | X | X | | X | | X | | X | | X | | X | | X | | X | | X | X |
| CBC w/diff, plts | X | X | | X | | X | | X | | X | | X | | X | | X | | X | X |
| Serum chemistry ² | X | X | | X | | X | | X | | X | | X | | X | | X | | X | X |
| TSH ³ | X | | | | | | | X | | | | | | X | | | | W 19 & Q6W | X |
| Amylase/ Lipase | X | | | | | | | | | | | | | | | | | | X |
| B-HCG ⁴ | X | | | | | | | X | | | | | | X | | | | W 19 & Q6W | X |
| EKG | X | | | | | | | | | | | | | | | | | | |
| Adverse Event Evaluation | X | X | | X | | X | | X | | X | | X | | X | | X | | X | X |
| Trial Imaging | X | | | | | | | | | X | | | | | | | | W 18 & Q12W | |
| Tumor Biopsy | X | | | | | | | | | | X | | | | | | | | |
| PD Blood Draw | X | X | | X | | X | | X | | | X | | | | | | | | X |

1. Includes blood pressure, heart rate, respiratory rate, oxygen saturation, and temperature
2. Albumin, alkaline phosphatase, total bilirubin, bicarbonate, BUN, calcium, chloride, creatinine, glucose, LDH, phosphorus, potassium, total protein, SGOT [AST], SGPT [ALT], sodium.
3. Reflex to Free T3 and T4 is TSH abnormal
4. Serum or urine pregnancy test (women of childbearing potential)
5. All screening procedures except labs to occur within 28 days of first dose. All labs to be collected within 14 days of first dose.

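### For an asymptomatic Grade 4 amylase or lipase elevation attributed to ipilimumab, one section stops ipilimumab permanently and two others let it resume; no on-treatment test is scheduled

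*Combined protocol and SAP*

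**What the plan says.** **Delay (Section 4.3.1).** Among the exceptions to the delay rule for Grade 3 laboratory abnormalities is: "Grade 3 lymphopenia or asymptomatic amylase or lipase elevation does not require dose delay". The same list ends with a discretionary clause: "Any AE, laboratory abnormality or intercurrent illness which, in the judgment of the investigator, warrants delaying the dose of study medication". The next paragraph holds both drugs until the restart criteria are met, and adds in parentheses: "Exceptions apply to the retreatment criteria after dose delay of ipilimumab and nivolumab for Grade" 3 or higher amylase and lipase abnormalities without pancreatitis that are attributed to ipilimumab alone.

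**Restart (Sections 4.3.3.1 and 4.3.3.2).** After a delay for such an abnormality, judged related to ipilimumab and not to nivolumab, participants "may resume nivolumab when the amylase or lipase abnormality has resolved to Grade < 3". For the other drug, "ipilimumab may only be resumed when the amylase or lipase abnormality resolves to Grade 1 or baseline". The ipilimumab condition appears in both sections.

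**Permanent discontinuation (Section 4.3.4.1).** The triggers include "Any Grade 4 drug-related adverse event or laboratory abnormality". The exceptions cover neutropenia, lymphopenia or leukopenia, isolated electrolyte abnormalities and endocrinopathies. Amylase and lipase are not among them. The section also says that the two drugs are assessed separately, and that nivolumab may continue when only ipilimumab meets the criteria.

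**Testing (Section 5).** Amylase and lipase are in the screening laboratory list (Section 5.1). They are absent from the dosing-visit list (Section 5.2) and the Day 28 follow-up list (Section 5.3). In the calendar (Section 5.4) the "Amylase/ Lipase" row is marked before treatment and at end of treatment only.

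**The concern.** The delay, restart and discontinuation rules are meant to sort each laboratory result into one action. For asymptomatic amylase and lipase elevations they do not clearly do so. At Grade 4, an investigator reading Section 4.3.4.1 ends ipilimumab, while one reading Section 4.3.3.2 waits for recovery and restarts it.

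These rules also concern elevations without symptoms. Nothing clinical prompts a test, so the rules work only if someone measures the enzymes, and the plan schedules no measurement between screening and end of treatment. At stake are uniform handling of patients with the same result and a usable record of why ipilimumab was held, restarted or stopped. Safety characterization is a secondary objective (Section 1.2, item D).

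**Working it through.** No sample size, error rate or event count is involved, so there is no formula to apply. Two checks were made.

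**Check 1: the rules by grade, for an asymptomatic elevation attributed to ipilimumab alone.**

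| Grade | Delay (4.3.1) | Restart (4.3.3.1, 4.3.3.2) | Permanent stop (4.3.4.1) |
|---|---|---|---|
| 3 | Not required; allowed at investigator judgment | Nivolumab below Grade 3; ipilimumab at Grade 1 or baseline | Not required: Grade 3 laboratory abnormalities are exempt apart from thrombocytopenia and liver tests |
| 4 | Not separately listed | Same thresholds, since the wording is Grade 3 or higher | Required; no amylase or lipase exception |

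- *Grade 4, ipilimumab.* The restart and stop columns give opposite outcomes for the drug to which the event is attributed.
- *Grade 4, nivolumab.* The restart rule applies only when nivolumab is judged not to be the cause, and Section 4.3.4.1 assesses each drug separately. The two columns can be read together without conflict.
- *Grade 3, both drugs.* No mandatory delay exists, so the restart thresholds can be reached only through the discretionary clause. That sequence is coherent, but no section says that the thresholds are limited to discretionary delays.

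Taken together, Grade 3 is exempt from mandatory delay and Grade 4 is a mandatory stop. No mandatory delay criterion leads to the situation that the restart rules describe.

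**Check 2: the test schedule.** The calendar has 20 columns: a row label and 19 time columns.

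| Row | Before treatment | Dosing columns marked | End of treatment |
|---|---|---|---|
| Nivolumab | – | 8 (weeks 1, 3, 5, 7, 9, 11, 13, 15) + 1 (week 17 and every 2 weeks) = 9 | – |
| Serum chemistry | Yes | 9 of 9 | Yes |
| Amylase and lipase | Yes | 0 of 9 | Yes |

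The amylase and lipase row has all 20 cells, so the blanks are not an extraction fault. The calendar footnote defining serum chemistry does not include the two enzymes, and the written lists in Sections 5.1 and 5.2 agree with the calendar.

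The end-of-treatment mark has no counterpart in the text. Section 5 describes only one visit after treatment stops, at Day 28, and its laboratory list in Section 5.3 omits both tests.

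**The case against.** Four arguments weigh on the other side.

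1. *Not requiring a delay does not forbid one.* This stands. A reader might infer that Section 4.3.1 contradicts the restart rules at Grade 3. The documents do not support that, because the discretionary clause allows a delay and the restart rules then say how it ends. What remains is that the link is left unstated.

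2. *The stop rule overrides.* The ipilimumab restart wording can be read as a necessary condition only, with the mandatory stop in Section 4.3.4.1 prevailing at Grade 4. That is a possible reading, but the restart text says Grade 3 or higher in three sections and nowhere excludes Grade 4. A reader needs to be told which rule prevails.

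3. *The drugs are assessed separately.* This stands for nivolumab. A reader might infer that the Grade 4 conflict covers both drugs; the attribution condition and the separate assessment in Section 4.3.4.1 do not support that. They do not help ipilimumab.

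4. *Testing on indication is enough.* Section 6.1 has signs of toxicity evaluated by laboratory studies where appropriate. Section 4.3.4.1 asks for laboratory studies at least every 6 weeks during delays beyond 6 weeks (12 for ipilimumab). Section 4.8.4 refers to label algorithms that are not reproduced. Unscheduled testing is therefore possible. None of this text names amylase or lipase as a test to be done, and testing on indication would miss some elevations that give no indication.

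A reader might also infer that the planned worst-grade laboratory tables will be distorted. Section 9 names hematology, coagulation, chemistry, liver function and renal function for those tables, but not amylase or lipase. The calendar also keeps these tests apart from serum chemistry, so the documents do not establish that consequence.

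**Conclusion.** The point holds in a limited form. For ipilimumab, an asymptomatic Grade 4 amylase or lipase elevation attributed to that drug has two opposite instructions. This rests on reading Grade 3 or higher literally and on the absence of these enzymes from the Grade 4 exceptions. At Grade 3 there is an unstated link rather than a contradiction, and for nivolumab no clear conflict.

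The schedule gap holds as described: none of the nine dosing columns carries the tests, and Section 5.3 does not match the calendar's end-of-treatment mark. The documents give no incidence for these elevations, so the number of affected patients among the planned 40 + 10 = 50 cannot be estimated.

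Neither the response-rate decision nor the definitions of progression-free and overall survival depend on these rules. The point is minor, but it leaves opposite instructions for one patient event and is easily removed.

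**What to change.** State in one place, by grade (3 and 4) and by drug, what follows an asymptomatic amylase or lipase elevation, and make Sections 4.3.1, 4.3.3.1, 4.3.3.2 and 4.3.4.1 agree with it. If the restart rules are meant only for delays at the investigator's judgment, say so. Whether Grade 4 falls within the restart rules or the stop rule is a clinical decision for the sponsor and investigator; this review takes no position on it.

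Then make Sections 5.2, 5.3 and 5.4 consistent with the rule kept, including the end-of-treatment mark that Section 5.3 does not carry.

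The cost is amendment wording. Any laboratory cost depends on the rule chosen; blood for chemistry is already drawn at every dosing visit.

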4.3.2. Dose Reductions

There will be no dose reductions for nivolumab or ipilimumab

4.3.3. Criteria to Resume Dosing

4.3.3.1 Criteria to Resume Nivolumab Dosing

Subjects may resume treatment with nivolumab when the drug-related AE(s) resolve(s) to Grade \leq 1 or baseline, with the following exceptions:

- Subjects may resume treatment in the presence of Grade 2 fatigue.
- Subjects who have not experienced a Grade 3 drug-related skin AE may resume treatment in the presence of Grade 2 skin toxicity.
- For subjects with Grade 2 AST, ALT, or Total bilirubin elevations, dosing may resume when laboratory values return to baseline and management with corticosteroids, if needed, is complete.
- Subjects with combined Grade 2 AST/ALT AND total bilirubin values meeting discontinuation parameters (see package insert) should have treatment permanently discontinued.
- Drug-related pulmonary toxicity, diarrhea, or colitis must have resolved to baseline before treatment is resumed. Subjects with persistent Grade 1 pneumonitis after completion of a steroid taper over at least 1 month may be eligible for retreatment if discussed with and approved by the PI.
- Subjects with Grade 1-3 drug-related endocrinopathies adequately controlled with only physiologic hormone replacement may resume treatment after consultation with the PI
- Subjects who received systemic corticosteroids for management of any drug-related toxicity must be off corticosteroids or have tapered down to an equivalent dose of prednisone \leq 10 mg/day.
- Participants who delay study treatment due to any Grade \geq 3 amylase or lipase abnormality that is not associated with symptoms or clinical manifestations of pancreatitis, and that is assessed by the investigator to be related to ipilimumab and not to nivolumab, may resume nivolumab when the amylase or lipase abnormality has resolved to Grade < 3. The PI should be consulted prior to resuming nivolumab in such participants.
- Dose delay of nivolumab that results in treatment interruption of > 6 weeks requires treatment discontinuation, with exceptions as noted in Section 4.3.4.
- One exception to note is when ipilimumab and nivolumab doses are delayed due to drug-related Grade \geq 3 amylase or lipase abnormalities not associated with symptoms or clinical manifestations of pancreatitis. If the investigator assesses the Grade \geq 3 amylase or lipase abnormality to be related to ipilimumab and not related to nivolumab, nivolumab may be

resumed when the amylase or lipase abnormality resolves to Grade < 3 but ipilimumab may only be resumed when the amylase or lipase abnormality resolves to Grade 1 or baseline. Investigator attribution of this toxicity to the ipilimumab dosing must be clearly noted in the participant's medical chart. The PI should be consulted prior to resuming nivolumab in such participants.

- If any of the above mentioned syndromes occur only after administration of nivolumab with ipilimumab and not after nivolumab-only doses, and the investigator feels that ipilimumab is the cause, nivolumab may be resumed if the above criteria are met

